### LSICM01: Listing of Pre-infusion Medications; Safety Analysis Set (Study 54767414MMY2036)

Treatment Group	Site ID	Subject ID	Visit	Start Date/Time (Study Day)	Medication Coded Term [Verbatim Term]	Dose (unit)	Route
Safety run-in	XXX	XXXXXXXX	CYCLE 1 DAY 1	2017-11-01T09:00 (1)	CLEMASTINE FUMARATE [TAVEGYL]	2 (mg)	INTRAVENOUS
			CYCLE 1 DAY 8	2017-11-08T09:00 (8)	CLEMASTINE FUMARATE [TAVEGYL]	2 (mg)	INTRAVENOUS
		XXXXXXXX	CYCLE 1 DAY 1	2017-11-01T09:00 (1)	CLEMASTINE FUMARATE [TAVEGYL]	2 (mg)	INTRAVENOUS

Programming note: please sort data by Treatment group (Safety run-in, Arm A, Arm B), site ID, subject ID, start Date/Time

### LSICM02: Listing of Post-infusion Medications; Safety Analysis Set (Study 54767414MMY2036)

Treatment Group	Site ID	Subject ID	Visit	Start Date (Study Day)	End Date (Study Day)	Medication Coded Term [Verbatim Term]	Dose (unit)	Route	Frequency
Safety run-in	XXX	XXXXXXXX	CYCLE 1 DAY	2017-11-01 (1)	2017-11-02 (2)	METHYLPREDNISOLONE [MEDROL]	20 (mg)	ORAL	Twice Daily
			CYCLE 1 DAY	2017-11-08 (8)	2017-11-08 (9)	METHYLPREDNISOLONE [MEDROL]	20 (mg)	ORAL	Twice Daily
		XXXXXXXX	CYCLE 1 DAY	2017-11-01 (1)	2017-11-02 (2)	METHYLPREDNISOLONE [MEDROL]	20 (mg)	ORAL	Twice Daily
		XXXXXXXX	CYCLE 1 DAY 1	2017-11-01 (1)	2017-11-02 (2)	METHYLPREDNISOLONE [MEDROL]	20 (mg)	ORAL	Twice Daily
			1						

Programming note: please sort data by Treatment group (Safety run-in, Arm A, Arm B), site ID, subject ID, Start date.

LSIPM01: List of Subjects with Prior Cancer-Related Surgery/Procedure; Safety Analysis Set (Study 54767414MMY2036)						
Treatment Group	Site ID	Subject ID	Description of Surgery or Procedure	Start Date	End Date	Indication

### Programming Notes:

1. Listing is sorted by treatment (Safety run-in, Arm A and Arm B), site ID, subject ID, start date of procedure.

LSIPM02: List of Prior Radiotherapy; Safety Analysis Set (Study 54767414MMY2036)								
Treatment	Site	Subject ID	Start Date	End Date	Location	Indication	Total Dose (Gy)	
Group	ID							

### Programming Notes:

- 1. Listing is sorted by treatment (Safety run-in, Arm A and Arm B), site ID, subject ID, start date of procedure.
- 2. If indication/location is "Other" and there is a specific description of the indication/location, then the specific description should be displayed

LSIDEV-ST01:	Listing of S	Subjects with M	ajor Protocol Deviations; Safety Analysis Set (Study 54767414MMY2036)	
Treatment Group	Site ID	Subject ID	Type of Protocol Deviation	Protocol Deviation Verbatim Term

### Programming Notes:

1. The sort order is Treatment Group (Safety run-in, Arm A and Arm B), Site ID, Subject ID, and Study Day of Deviation.

# TSIEX-ST01: Summary of Treatment Cycles, Duration of Study Treatment and Dose Intensity; Safety Analysis Set (Study 54767414MMY2036)

nalysis set: Safety	####	###	###
uration of treatment (months)			
N	###	###	###
Mean (SD)	xx.x (xx.xx)	xx.x (xx.xx)	xx.x (xx.xx)
Median	XX.X	XX.X	XX.X
Range	(xx;xx)	(xx;xx)	(xx;xx)
imber of treatment cycles			
N (CD)	###	###	###
Mean (SD)	xx.x (xx.xx)	xx.x (xx.xx)	xx.x (xx.xx)
Median	XX.X	XX.X	XX.X
Range	(XX;XX) ## (XX X0/)	(XX;XX) ## (XX X9/)	(XX;XX) ## ( XX X 9/)
$\geq 1$ cycle	## (XX.X%)	## (XX.X%)	## (XX.X%)
$\geq 2$ cycles	## (XX.X%)	## (XX.X%)	## (XX.X%)
$\geq$ 3 cycles	## (XX.X%)	## (XX.X%)	## (XX.X%)
$\geq$ 4 cycles	## (XX.X%)	## (XX.X%)	## (XX.X%)
$\geq$ 5 cycles	## (XX.X%)	## (XX.X%)	## (XX.X%)
tal number of daratumumab infusions			
N	###	###	###
Mean (SD)	xx.x (xx.xx)	xx.x (xx.xx)	xx.x (xx.xx)
Median	XX.X	XX.X	XX.X
Range	(xx;xx)	(xx;xx)	(xx;xx)
tal dose of daratumumab (mg/kg)			
N	###	###	###
Mean (SD)	xx.x (xx.xx)	xx.x (xx.xx)	xx.x (xx.xx)
Median	XX.X	XX.X	XX.X
Range	(xx;xx)	(xx;xx)	(xx;xx)
ose intensity for daratumumab (mg/kg/cycle)			
N	###	###	###
Mean (SD)	xx.x (xx.xx)	xx.x (xx.xx)	xx.x (xx.xx)
Median	XX.X	XX.X	XX.X
Range	(xx;xx)	(xx;xx)	(xx;xx)
elative dose intensity for daratumumab (%)			
N	###	###	###
Mean (SD)	xx.x (xx.xx)	xx.x (xx.xx)	xx.x (xx.xx)
Median	XX.X	XX.X	XX.X
Range	(xx;xx)	(xx;xx)	(xx;xx)
(1) (1) (1) (1) (1) (1) (1) (1) (1) (1)			
otal number of JNJ-63723283 infusions	###	###	###
Mean (SD)	xx.x (xx.xx)	xx.x (xx.xx)	xx.x (xx.xx)
Median	XX.X	XX.X	XX.X
Range	(xx;xx)	(xx;xx)	(xx;xx)
tal dose of JNJ-63723283 (mg)			
Ν	###	###	###
Mean (SD)	xx.x (xx.xx)	xx.x (xx.xx)	xx.x (xx.xx)
Median	XX.X	XX.X	XX.X
Range	(xx;xx)	(xx;xx)	(xx;xx)

# TSIEX-ST01: Summary of Treatment Cycles, Duration of Study Treatment and Dose Intensity; Safety Analysis Set (Study 54767414MMY2036)

Dose intensity for JNJ-63723283 (mg/cycle) b			
N	###	###	###
Mean (SD)	xx.x (xx.xx)	xx.x (xx.xx)	xx.x (xx.xx)
Median	XX.X	XX.X	XX.X
Range	(xx;xx)	(xx;xx)	(xx;xx)
Relative dose intensity for JNJ-63723283 (%)			
N	####	###	###
Mean (SD)	xx.x (xx.xx)	xx.x (xx.xx)	xx.x (xx.xx)
Median	XX.X	XX.X	XX.X
Range	(xx;xx)	(xx;xx)	(xx;xx)

a Dose intensity (mg/kg/cycle) is calculated as the sum of total doses (mg/kg) received in all cycles divided by the number of treatment cycles on daratumumab.

b Dose intensity (mg/cycle) is calculated as the sum of total doses (mg) received in all cycles divided by the number of treatment cycles on JNJ-63723283.

Note: The relative dose intensity (%) is the ratio of total actually received dose and total planned dose.

### TSIEXP02: Summary of Treatment Cycle Delays, Incidences of and Reasons for Study Treatment Dose Modifications; Safety Analysis Set (Study 54767414MMY2036)

Analysis set: Safety	##	##
Subjects with cycle delays	## (XX.X%)	## (XX.X%)
Reason for cycle delays		
Adverse event	## (XX.X%)	## (XX.X%)
Other	## (XX.X%)	## (XX.X%)
Subjects with dose delays		
Daratumumab	## (XX.X%)	## (XX.X%)
Reason for delays		
Adverse event	## (XX.X%)	## (XX.X%)
Other	## (XX.X%)	## (XX.X%)
JNJ-63723283	## (XX.X%)	## (XX.X%)
Reason for delays		
Adverse event	## (XX.X%)	## (XX.X%)
Other	## (XX.X%)	## (XX.X%)
Subjects with dose skipped		
Daratumumab	## (XX.X%)	## (XX.X%)
Reason for skipping		
Adverse event	## (XX.X%)	## (XX.X%)
Other	## (XX.X%)	## (XX.X%)

### TSIEXP02: Summary of Treatment Cycle Delays, Incidences of and Reasons for Study Treatment Dose Modifications; Safety Analysis Set (Study 54767414MMY2036)

J-63723283	## (XX.X%)	## (XX.X%)
Reason for skipping		
Adverse event	## (XX.X%)	## (XX.X%)
Other	## (XX.X%)	## (XX.X%)

Note: Percentages calculated with the number of subjects in each group as denominator.

# TSIEXP03: Summary of Action Taken During the Infusion; Safety Analysis Set (Study 54767414MMY2036)

Analysis set: Safety	##	##
Subjects with infusion interrupted		
Daratumumab	## (XX.X%)	## (XX.X%)
Reason for infusion interrupted		
Adverse event	## (XX.X%)	## (XX.X%)
Other	## (XX.X%)	## (XX.X%)
JNJ-63723283	## (XX.X%)	## (XX.X%)
Reason for infusion interrupted		
Adverse event	## (XX.X%)	## (XX.X%)
Other	## (XX.X%)	## (XX.X%)
Subjects with infusion rate decreased		
Daratumumab	## (XX.X%)	## (XX.X%)
Reason for infusion rate decreased		
Adverse event	## (XX.X%)	## (XX.X%)
Other	## (XX.X%)	## (XX.X%)
JNJ-63723283	## (XX.X%)	## (XX.X%)
Reason for infusion rate decreased		
Adverse event	## (XX.X%)	## (XX.X%)
Other	## (XX.X%)	## (XX.X%)
Subjects with infusion aborted		
Daratumumab	## (XX.X%)	## (XX.X%)
Reason for infusion aborted		
Adverse event	## (XX.X%)	## (XX.X%)
Other	## (XX.X%)	## (XX.X%)
JNJ-63723283	## (XX.X%)	## (XX.X%)
Reason for infusion aborted		
Adverse event	## (XX.X%)	## (XX.X%)
Other	## (XX.X%)	## (XX.X%)

### LSIEX-ST01: Listing of Treatment Exposure; Safety Analysis Set (Study 54767414MMY2036)

											Reason for	
					Infusion				Reason for		Action	
					Date	Total		Action Planned	Action Planned	Action Taken	Taken	If 'INFUSION
Treatment	Site	Subject	Study		(Study	Dose	Start/End	Prior to Infusion	Prior to	During	During	INTERRUPTED' , Interruption
Group	ID	ĪĎ	Drug	Visit	Day)	(mg)	Time	Start	Infusion Start	Infusioin	Infusion	Start/End Time

Programming Notes:

The sort order is Treatment Group (Safety run-in, Arm A, Arm B), Site ID, Subject ID, Study Drug and Infusion Date

### LEFRSP01: Listing of Efficacy Variable Based on Investigator Assessment; Safety Analysis Set (Study 54767414MMY2036)

									Date of Last			
Treatm					Date of Best Resp.	Date of		Reason	Disease		Date of Death/	
ent		Subject	Measurable	Best	(Study Day)	PD	Reason	for PD	Assessment	PFS	Last Date Known to be	OS
Group	Site ID	IĎ	Disease Type	Resp.		(Study Day)	for PD	Censoring	(Study Day)	(Month)	Alive (Study Day)	(Month)
Arm A	XX	XX	Serum	CR	2018-06-04 (XX)			XX	2018-06-14 (xx)	2.4+	2018-06-14 (xx)	2.4+
Key: sCR	=stringent co	mplete respo	nse; CR=complete	response; V	GPR=very good partial r	esponse; PR=parti	al response;	MR=minimal re	sponse; SD=stable di	sease; PD=pi	rogression disease; NE=not e	valuable.

Key: sCR=stringent complete response; CR=complete response; VGPR=very good partial response; PR=partial response; MR=minimal response; SD=stable disease; PD=progression disease; NE=not evaluable. Key: OS=Overall Survival; PFS=Progression-free Survival; Resp.=Response. +: Censoring.

Programming notes:

Sort the listing by Treatment group (Arm A, Arm B), Site ID, and Subject ID.

Analysis set: Safety	###	###	###	###
Any TEAE	### (xx.x%)	### (xx.x%)	### (xx.x%)	### (xx.x%)
At least one related a	### (xx.x%)	### (xx.x%)	### (xx.x%)	### (xx.x%)
At least one related to daratumumab	### (xx.x%)	### (xx.x%)	### (xx.x%)	### (xx.x%)
At least one related to JNJ-63723283 Maximum toxicity grade	### (xx.x%)	### (xx.x%)	### (xx.x%)	### (xx.x%)
Grade 1	### (xx.x%)	### (xx.x%)	### (xx.x%)	### (xx.x%)
Grade 2	### (xx.x%)	### (xx.x%)	### (xx.x%)	### (xx.x%)
Grade 3	### (xx.x%)	### (xx.x%)	### (xx.x%)	### (xx.x%)
Grade 4	### (xx.x%)	### (xx.x%)	### (xx.x%)	### (xx.x%)
Grade 5	### (xx.x%)	### (xx.x%)	### (xx.x%)	### (xx.x%)
Any serious TEAE	### (xx.x%)	### (xx.x%)	### (xx.x%)	### (xx.x%)
At least one related a	### (xx.x%)	### (xx.x%)	### (xx.x%)	### (xx.x%)
At least one related to daratumumab	### (xx.x%)	### (xx.x%)	### (xx.x%)	### (xx.x%)
At least one related to JNJ-63723283	### (xx.x%)	### (xx.x%)	### (xx.x%)	### (xx.x%)
FEAE leading to discontinuation of study reatment $^{b}$	### (xx.x%)	### (xx.x%)	### (xx.x%)	### (xx.x%)
TEAE leading to discontinuation of laratumumab	### (xx.x%)	### (xx.x%)	### (xx.x%)	### (xx.x%)
At least one related to daratumumab	### (xx.x%)	### (xx.x%)	### (xx.x%)	### (xx.x%)
TEAE leading to discontinuation of JNJ-	### (xx.x%)	### (xx.x%)	### (xx.x%)	### (xx.x%)
53723283 At least one related to JNJ-63723283	### (xx.x%)	### (xx.x%)	### (xx.x%)	### (xx.x%)
FEAE with outcome of death	### (xx.x%)	### (xx.x%)	### (xx.x%)	### (xx.x%)
At least one related to daratumumab	### (xx.x%)	### (xx.x%)	### (xx.x%)	### (xx.x%
At least one related to JNJ-63723283	### (xx.x%)	### (xx.x%)	### (xx.x%)	### (xx.x%)

# TSFAE-ST01: Overview of Treatment-emergent Adverse Events; Safety Analysis Set (Study 54767414MMY2036)

Key: TEAE = treatment-emergent adverse event.

a TEAEs related to at least 1 of the 2 study treatments: daratumumab and JNJ-63723283.

b Includes those subjects indicated as having discontinued treatment due to an adverse event on the end of treatment CRF page. Note: Adverse events are coded using MedDRA version XX.X. Percentages are calculated with the number of subjects in each group as denominator.

Display Specifications	
Output Identifier	TSFAE01
Programming Notes:	

- 1. TEAE with outcome of death are based on an AE outcome equal to Fatal or toxicity grade of 5 from AE page.
- 2. An AE is considered to result in discontinuation of study agent if the "action taken regarding study agent" is "drug withdrawn" on the AE eCRF page. If an attribute of the AE is missing, it will not be imputed.
- 3. An AE is considered to result in discontinuation of study treatment if the reason for termination on the End of Treament disposition page is AE.

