## **OVERVIEW OF STUDY DESIGN**

This is a randomized, multicenter, multiphase study assessing the anti-tumor activity and safety of JNJ-63723283 administered in combination with daratumumab, compared with daratumumab alone in subjects with relapsed or refractory multiple myeloma. Subjects 18 years and older with multiple myeloma who have received at least 3 prior lines of therapy including a proteasome inhibitor (PI) and an immunomodulatory inhibitor (IMiD) or whose disease is double refractory to both a PI and an IMiD are eligible. Approximately 6 subjects will be enrolled in Part 1 (a safety run-in cohort) followed by 80 subjects randomly assigned in a 1:1 ratio to the 2 treatment arms in Part 2 (Phase 2). After all subjects in Part 2 are followed-up for approximately 4 months or discontinue earlier, the Sponsor will review all available data and decide whether to initiate Part 3 (Phase 3) of this study, where an additional 300 subjects will be randomly assigned in a 1:1 ratio to the 2 treatment arms.

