## 1.2. Analysis Sets

- Safety analysis set: includes all subjects who have received at least 1 dose of study agent (JNJ-63723283 or daratumumab, partial or complete) in either Safety Run-in Part 1 or Part 2 of the study. This analysis set will be used for below analyses.
- **Pharmacokinetics (PK)-evaluable analysis set:** includes all subjects who have received at least 1 dose of daratumumab or JNJ-63723283 and have at least 1 post-infusion sample in Safety Run-in Part 1 of the study.
- **Immunogenicity analysis set:** include all subjects who have received at least 1 dose of JNJ-63723283 or daratumumab and have appropriate serum samples for detection of antibodies to JNJ-63723283 or daratumumab (i.e., subjects with at least 1 sample obtained after their first dose of JNJ-63723283 or daratumumab) in Safety Run-in Part 1 of the study.

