## 1.3. Treatment Groups

The treatment groups are Safety Run-in (JNJ-63723283+daratumumab); and Arm A (daratumumab alone) and Arm B (JNJ-63723283+ daratumumab) for Part 2.

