## 1.7. Safety

### • Adverse events:

- An overview of treatment-emergent adverse events (TEAEs) will be summarized for safety population by treatment group and overall.
- Incidence of TEAEs will be summarized by MedDRA SOC, and preferred term.
- List of subjects with any TEAEs, serious TEAEs, toxicity grade 3 or 4 TEAEs, treatmentemergent Infusion Related Reactions (IRRs), and immune-mediated TEAEs will be provided for safety population.
- List of subjects with any TEAEs leading to all treatment discontinuation, TEAEs leading to any treatment discontinuation, TEAEs with outcome death, TEAEs leading to cycle delay or dose modifications, and TEAEs leading to infusion interrupted, infusion rate decreased or infusion aborted will be provided for safety population.
- Subjects who died during the study, and had new malignancies will also be listed, respectively.
- Laboratory values: Laboratory values will be listed at each time points for safety analysis set.
  - The hematology parameters include: hemoglobin, lymphocytes, neutrophils, platelet, and white blood cell (WBC).
  - The chemistry parameters include: alanine aminotransferase (ALT), alkaline phosphatase, aspartate aminotransferase (AST), amylase, calcium, creatinine, creatinine clearance, potassium, sodium, total bilirubin, and total lipase,
  - The thyroid function parameters include: free thyroxine, free triiodothyronine, thyroid stimulating hormone, and total triiodothyronine.
- Electrocardiograms (ECG): ECG values will be reported at each time points for safety analysis set in listings.
- Vital signs: Vital signs will be listed at each time points for safety analysis set. The variables include: weight, blood pressure (systolic and diastolic).

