## 3. COLUMN LAYOUTS FOR TABLES

All tables listed in Section 2 are to be presented with the following columns layout, unless specified otherwise.

Layout 1: To be used in demographics, baseline disease characteristics, prior systemic therapies, medical history, TEAE overview, safety.

Safety Run-in Phase 2		Total
	Arm A	

Layout 2: To be used in exposure tables.

Safety Run-in	Phase 2
	Arm A

Layout 3: To be used in PK tables

Layout 4: To be used in immunogenicity tables

Safety Run-in

Programming notes:

 Footnotes that correspond to the naming of the treatment groups are specified as below: Key: Arm A = daratumumab alone;

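### In the TEAE overview (TSFAE01), the Total percentages for the five JNJ-63723283-specific rows are divided by all treated subjects, including Arm A subjects never given that drug, so they are not rates among exposed subjects

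*SAP*

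**What the plan says.** SAP Section 1.7 states: "An overview of treatment-emergent adverse events (TEAEs) will be summarized for safety population by treatment group and overall". SAP Section 2 assigns TSFAE01 to column layout 1. Section 3 describes that layout as "Layout 1: To be used in demographics, baseline disease characteristics, prior systemic therapies, medical history, TEAE overview, safety", and its header ends in a Total column.

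The population behind the Total is the safety set of SAP Section 1.2, which "includes all subjects who have received at least 1 dose of study agent (JNJ-63723283 or daratumumab, partial or complete"), in Part 1 or Part 2. SAP Section 1.3 defines the Part 2 groups as "Arm A (daratumumab alone) and Arm B (JNJ-63723283+ daratumumab) for Part 2". Arm A subjects are therefore in the safety set without being assigned JNJ-63723283.

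The TSFAE-ST01 shell prints a count and percentage in every column, including for these five rows:

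- any TEAE: "At least one related to JNJ-63723283";
- any serious TEAE: the same sub-row;
- "TEAE leading to discontinuation of JNJ"-63723283;
- under that row, at least one such event related to JNJ-63723283;
- TEAE with outcome of death: the sub-row for relation to JNJ-63723283.

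The table note gives one denominator rule for all rows: "Percentages are calculated with the number of subjects in each group as denominator". None of the three programming notes restricts these rows to JNJ-63723283 recipients or marks Arm A as not applicable.

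**The concern.** A percentage of subjects with an event attributed to a drug is naturally read as a rate among people who took the drug. In the Total column these five rows do not have that meaning. Arm A subjects can add to the denominator but never to the numerator, so the printed percentage depends on how many control subjects happened to be treated as well as on how the drug was tolerated.

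This is the first study of the combination, and the table is marked for in-text use. Protocol Section 10.2 sets drug-related event incidence beside marketed anti-PD-1 products and the single-agent Phase 1 study, so these are figures that someone may carry into a cross-study comparison. A reader who lifts the Total percentage would quote a number that errs in one direction only, towards fewer JNJ-63723283-related events.

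**Working it through.** **Plan's own figure.** The documents give no rate, power or sample size that bears on this table, so there is nothing to reproduce. The check is direct arithmetic on the denominator rule.

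**Inputs**

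- Denominator: column N for every row (TSFAE-ST01 note).
- Total column: required by SAP Section 1.7 and shown in Layout 1. The column headers of the TSFAE-ST01 shell itself are missing from the text available to us, so the Total is established from these two sections.
- Total population: everyone given either drug (SAP Section 1.2).
- Arm A exposure to JNJ-63723283: none (SAP Section 1.3).
- Actual treated counts: not given. Protocol Section 11.12 says only that the number is small.
- Planned run-in size: about 6 (Protocol Synopsis).

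**Formula.** Let E be the number of subjects in the Total who received JNJ-63723283, U the number who did not, and x the number with the event. Then x comes only from E.

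- Rate among exposed = x / E
- Printed Total percentage = x / (E + U)
- Ratio of the second to the first = E / (E + U), which is below 1 whenever U is at least 1

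**Case 1 (assumed): E = 6 run-in subjects, no Arm B subjects treated, x = 3, so the exposed rate is 3/6 = 50.0%.**

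| Arm A subjects (U) | Factor E/(E+U) | Printed Total |
|---|---|---|
| 1 | 6/7 = 0.86 | 3/7 = 42.9% |
| 3 | 6/9 = 0.67 | 3/9 = 33.3% |
| 6 | 6/12 = 0.50 | 3/12 = 25.0% |

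**Case 2 (assumed): 6 run-in subjects plus equal numbers treated in Arms A and B.** The exposed subjects now include Arm B, so the dilution is milder.

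| Per arm | Factor |
|---|---|
| 1 | 7/8 = 0.88 |
| 3 | 9/12 = 0.75 |
| 5 | 11/16 = 0.69 |

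**What is not affected.** The daratumumab rows are unaffected because every group is assigned daratumumab. The Safety Run-in column, and an Arm B column if there is one, contain no Arm A subjects. The counts in the Total column are correct, because adding unexposed subjects adds zero events. Only the Total percentages in these five rows change.

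**The case against.** The strongest reply is that the table misstates nothing. The column is a total over all treated subjects, the footnote discloses the denominator, and every cell shows a count beside the percentage. The figure is a correct proportion of everyone treated, and the SAP nowhere calls it the JNJ-63723283 toxicity rate. The undiluted rate stands in the same row, in the Safety Run-in column. Layout 1, as it survives in the text, shows only Arm A under Phase 2. If that is the final layout, a corrected Total would merely repeat the run-in column. The analysis is descriptive, with no hypothesis testing (Protocol Section 11.12), and Part 3 has been dropped. The run-in decision rested on DLT counts reviewed by the safety evaluation team. The adverse event listing gives relationship to, and action taken with, each drug for every subject, so an exposed-only rate can be recovered exactly.

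All of that stands as a limit on consequence. It does not give the Total percentage in these rows a useful meaning: it answers neither how often recipients had the event nor how the arms differ.

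A reader might draw three stronger conclusions, and the documents do not support them:

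- **That the trial's JNJ-63723283 toxicity is understated generally.** It is not. The group columns, counts and listings carry the correct information.
- **That the Total runs at about half the exposed rate because the planned sizes give 46/86 = 0.53.** The Protocol Synopsis does plan that "Approximately 6 subjects will be enrolled in Part 1 (a safety run-in cohort) followed by 80 subjects randomly assigned in a 1:1 ratio", giving 6 + 40 exposed of 86. Enrollment closed on 25 May 2018, however, and the SAP was approved on 25 September 2018 for a trial with few treated subjects. Planned sizes cannot describe this table.
- **That the SAP deliberately avoids the problem elsewhere.** Layout 2 shows no Total for exposure tables, but the SAP gives no denominator reason for this, and the TSIEXP02 shell applies column N to its own JNJ-63723283 rows. The antibody tables restrict to subjects with post-dose samples because a sample is needed to be evaluable, which is a different matter.

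**Conclusion.** The point holds for the Total percentages in five rows of one table. As specified, they are not rates among exposed subjects and are too low by the factor exposed/total whenever at least one Arm A subject is treated. The direction is certain under that condition. The size is not, because treated counts are not in the documents: it is 0.86, 0.67 or 0.50 on the assumption of 6 exposed run-in subjects, no Arm B subjects and 1, 3 or 6 Arm A subjects, and closer to 1 if Arm B subjects were also treated. No formal decision depends on these cells. The severity is minor: a presentation fault to correct before the table is quoted in text, and no reason to doubt the safety data.

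**What to change.** In TSFAE-ST01, add a rule for the five JNJ-63723283-specific rows: the Total denominator is the number of subjects who received at least one dose of JNJ-63723283, and the Arm A cells read 'not applicable'. Alternatively, leave the Total blank in those rows. If the run-in turns out to be the only exposed group, this loses nothing. Amend the table footnote so that it states the exception alongside the general column-N rule, and print the restricted N if the Total is kept.

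Defining the denominator by drug received, not by assigned group, also covers a combination subject given daratumumab on Cycle 1 Day 1 who never went on to JNJ-63723283. The documents do not say whether any such subject exists.

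The cost is one footnote and one denominator rule in the table program. No new data are needed, and no other output changes.
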